Mystical Experience and Anxiety: Finally, we wish to examine the association between undergoing a peak or mystical experience during psilocybin-assisted psychotherapy and subsequent reduction in anxiety. Presence and features of mystical experiences will be measured via a self-report instrument administered 24 hours after each experimental session, and self-boundary changes will be assessed via a self-report instrument administered at baseline, 24 hours after each experimental session and two weeks after the second experimental session. When applicable, occurrence of mystical experiences and changes in self-boundary will be assessed 24 hours after each open-label session.

General Investigational Plan

Drug Description and Doses

Participants will either receive 4 or 25 mg psilocybin (4-phosphoryloxy- N,N-dimethyl-tryptamine) in opaque capsules on two separate psilocybin-assisted psychotherapy sessions to occur seven to 14 days apart.

The full experimental intervention dose of psilocybin was chosen on the basis of early psilocybin psychotherapy research (Passie 2005) and recent studies of psilocybin's ability to produce mystical or spiritual experiences in healthy individuals with prior spiritual practice (Griffiths et al. 2006; Hasler et al. 2004). The dose is slightly lower on average than Griffiths and colleagues' dose of 30 mg/70 kg and is expected to produce all the cardinal effects of serotonergic hallucinogens, including changes in visual perception, rapid and sometimes profound changes in mood, derealization and depersonalization (feeling as if the world or the self are not real, feeling "as if in a dream") and unusual experiences relating to the body and the self. These effects are expected to facilitate therapeutic effects, including generation of a peak or mystical experience, reassessment of world view, perception of the body or the self, and re-appraisal or feelings of mastery over anxiety. This dose is also expected to overcome any potential blunting of effects arising from concurrent use of opiates in pain management medication (Grob 2007).

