The active placebo in this study will be a low dose of the investigational drug. Active placebo dose of psilocybin was chosen on the basis of early and recent studies of psilocybin in humans (Hasler et al. 2004; Isbell 1959; Moreno et al. 2006; Passie et al. 2002). This dose was chosen for its ability to produce a few of the effects of psilocybin without producing any of the potentially therapeutic effects. People may perceive lights or colors as being brighter and sounds as being different, and they may experience slight changes in mood, cognition or perception. A 4 mg dose of psilocybin is not expected to generate a mystical or transformative experience.

Sample Population and Subjects

The study will enroll nine (9) individuals with the following criteria listed below. Study drop-outs or withdrawals will be replaced until nine participants have completed the randomized phase of the study. Study completion will be defined as attending visits from screening up through the follow-up two weeks after the second psilocybin-assisted session. Participants who are unable to complete or withdraw from the open-label phase or before the two-month follow-up phase will not be replaced. Inclusion Criteria

Inclusion Criteria

Prospective participants must meet the following inclusion criteria listed below to be eligible for study enrollment.

1. Have been diagnosed with Stage IV melanoma with a life expectancy of one year or less
2. Meet diagnostic criteria for anxiety on the SCID, or a score of 8 or higher on the HADS Anxiety score.
3. Diagnosis must be a new diagnosis of anxiety subsequent to diagnosis with melanoma.
4. Are 18 years or older,
5. Live with another adult who is their primary caregiver, who can also provide transportation to and from the cancer center for each experimental session and who also consents to take part in a parallel investigation of anxiety and depression in primary caregivers. The same caregiver may remain overnight with participants after each psilocybin session.
6. Have a Mini-Mental State Exam score of 27 or higher.
7. Are willing to commit to medication dosing, experimental sessions with overnight stay, traveling to follow-up sessions, and to complete the evaluation instruments.
8. Are willing to refrain from taking any anti-depressants during the study period.
9. Are willing to refrain from taking any benzodiazepines during the 24 hours preceding each scheduled psilocybin, placebo, or open label session.

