After giving written consent, participants will be screened for presence of anxiety and for the presence of any psychiatric conditions that preclude study participation, such as psychosis. The principal investigator will conduct the screening evaluation in his office. The Structured Diagnostic Clinical Interview (SCID) will be used for diagnosing anxiety and detecting any conditions that preclude study participation, and the Mini Mental State Evaluation (MMSE) will be used to determine mental state and competency to take part in the study. Only participants with MMSE scores of 27 or higher will be eligible for study participation. The Hospital Anxiety and Depression Scale (HADS) will be used to quantify anxiety. Only people who are diagnosed with anxiety via SCID or who have a HADS Anxiety score of eight (8) or higher will be eligible for study participation. Once it is determined that participants meet study eligibility criteria, participants will complete or undergo additional assessments of anxiety and depression, quality of life and functional status, described above. The primary caregivers will complete the HADS. The investigators will also provide participants with daily pain and medication diaries and instructions on how to complete them. Participants will begin completing daily pain and medication diaries starting after baseline analysis.

Randomized blinded Study phase

Randomization

Upon enrollment into the study, participants will be assigned to one of two conditions, active placebo (4 mg psilocybin) or full experimental intervention (25 mg psilocybin). Active placebo in this study is a low dose of the investigational drug that will not produce the unique effects of psilocybin. Participants have a 66% chance of assignment to the full experimental intervention, with six of nine participants will be assigned to receive the full experimental intervention and three will be assigned to receive active placebo. The internal review committee coordinator at the study site will generate and maintain the randomization code and procedure. Condition assignment will be maintained from study enrollment up through the course of the study, as there is no crossover design. If there is an adverse event or other emergency requiring knowledge of participant's condition assignment, as when pharmacological intervention is necessary, the blind may be broken for an individual participant.

Introductory Psychotherapy Session (Visits #4 and #4.5)

Psychotherapy

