If at least four participants complete measures during the follow-up two months after the second experimental or open-label psilocybin-assisted therapy session, then the investigators will perform separate repeated-measures ANOVAs on the anxiety, depression, quality of life and spirituality scores listed above, with p. set at 0.05. The investigators are chiefly interested in differences between baseline and two-month follow-up scores. If a sufficient number of participants complete pain measures on the date of the two-month follow-up session, then the investigators will perform a t-test to compare VAS pain ratings on the day of the two-month follow-up with the average pre-psilocybin pain rating.

Given that only three participants will be eligible for the open-label phase of the study, the investigators do not plan to perform formal comparisons between anxiety, depression, spirituality or quality of life across the randomized and open-label study phases. However, the investigators will perform informal observations and present descriptive statistics for all outcome variables two weeks after the second open-label psilocybin-assisted session.

Before analyzing differences between degree of mystical experiences or changes in spiritual identity for active placebo and experimental dose participants, the investigators will first perform a matched-sample t test to determine whether there were significant differences between mystical experience (SCQ) and self-concept boundary/spiritual identity (SELF) scores measured after each of the two psilocybin-assisted sessions. If there are no significant differences between SCQ and SELF scores after the first and the second psilocybin session, then the investigators will compute the average between the two scores and employ the average SCQ and SELF score in nearly all subsequent analyses of these scores. Subsequent analyses will include an analysis of variance comparing SCQ and SELF scores in active placebo and full-dose participants, and correlational analyses of anxiety (HADS and STAI) and depression (HADS) scores as related to SCQ and SELF scores, with p. set at 0.05. The investigators may also compare

SCQ scores and NK cell counts made from blood sampled approximately 23 hours after each psilocybin-assisted session to see whether there are associations between presence and degree of mystical experience changes in immunological function.

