Risks of Active Placebo dose of Psilocybin

The 4 mg dose of psilocybin used in this study is expected to produce some but not most of the effects of the full 25 mg dose. These include slight changes in perception, cognition or mood, such as slight increases in positive or negative mood or lights or colors seeming brighter. This dose is not expected to produce potentially therapeutic effects, such as amplifying or generating intense mystical or transformative experiences. When combined with psychotherapy, the active placebo dose is not expected to reduce anxiety to the same degree as the experimental intervention dose. It is necessary to employ an active placebo so as to have a controlled study and to maintain the blind concerning condition assignment. Participants who learn they received active placebo will have the opportunity to consent to undergo an open-label study continuation immediately upon learning that they received active placebo.

Alternative Treatments and Procedures

The primary alternative to study participation is not to take part in the study. There are a number of recognized treatments for anxiety arising from diagnosis with a potentially fatal illness such as stage IV melanoma. Treatment often includes both psychotherapy and medication. Most commonly recommended psychotherapeutic treatments include stress management, cognitive therapy, exposure therapy, and psychodynamic psychotherapy. Medications that may ameliorate symptoms of anxiety include

antidepressants (SSRI or tricyclic), benzodiazepines, and mood stabilizers. Participation in this study is entirely voluntary, and refusing to take part in this study will not affect the care the participant is already receiving for anxiety arising from advanced stage illness. Nor will declining to participate affect any care he or she is receiving for stage IV melanoma. Participants will not be penalized for withdrawing from the study.

Confidentiality

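### The planned correlation of SCQ with anxiety names no arm term, so a pooled test would mix the dose effect with any link between mystical experience and anxiety reduction

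*Protocol*

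**What the plan says.** The last of the Secondary Objectives (Mystical Experience and Anxiety) is to examine "the association between undergoing a peak or mystical experience during psilocybin-assisted psychotherapy and subsequent reduction in anxiety".

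Data Analysis sets out the matching tests. SCQ and SELF are first compared between arms by analysis of variance. The same sentence then adds "correlational analyses of anxiety (HADS and STAI) and depression (HADS) scores as related to SCQ and SELF scores, with p. set at 0.05". It gives the variables and the significance level. It does not mention arm, a stratum or a single-dose subset, and it speaks of scores without saying whether change is meant or which visit supplies them.

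On what dose is expected to do:
- Under Drug Description and Doses, the protocol says of the 25 mg dose's effects: "These effects are expected to facilitate therapeutic effects, including generation of a peak or mystical experience".
- The same section says of the low dose: "A 4 mg dose of psilocybin is not expected to generate a mystical or transformative experience".
- Risks of Active Placebo dose of Psilocybin adds that "the active placebo dose is not expected to reduce anxiety to the same degree as the experimental intervention dose".

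Under Randomization, "six of nine participants will be assigned to receive the full experimental intervention and three will be assigned to receive active placebo".

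Before these analyses, a matched t test decides whether the two sessions are averaged. The averaging rule opens "If there are no significant differences between SCQ and SELF scores after the first and the second psilocybin session", and no rule is given for a significant result.

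**The concern.** On the protocol's own expectations, randomised dose moves both variables: SCQ up and anxiety down at 25 mg, with less of each at 4 mg. If all nine participants go into one correlation, that shared cause produces a negative r even when, among people given the same dose, those with stronger experiences do no better than the rest. The pooled test cannot separate a link between experience and relief from a difference between the arms.

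There is also a mismatch of variable. The objective is reduction in anxiety, whereas the analysis correlates scores. HADS is collected at V3, V4, V5, V7, V8 and V10 (Time and Events), so the choice of visit and of score or change is open.

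What is at stake is the trial's mechanism question. The Rationale says the sponsor will use its pilot studies to decide on Phase 3 population, drug and dosing, so a correlation that partly reflects dose could be carried forward as evidence about mechanism.

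**Working it through.** **Inputs.** Allocation is 6:3 (Randomization). The effect size is 0.4 to 0.7, with 0.6 used (Statistical Power). Alpha is 0.05, taken as two-sided because sidedness is not stated. The protocol gives no separation between arms on SCQ; 2 to 4 SD is assumed and the range is shown.

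**The protocol's own figure.** For a two-sample t test with 6 and 3 participants and d = 0.6, the noncentrality is 0.6 / √(1/6 + 1/3) = 0.849 on 7 df, with critical t 2.365. Power is 0.1143, as stated. This confirms that 0.6 is a mean difference in SD units. The protocol gives no figure for the correlation itself.

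**Expected pooled correlation with no within-dose link.** Let dS and dA be the arm gaps on SCQ and anxiety in SD units, with pq = (6/9)(3/9) = 2/9:

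r = -pq·dS·dA / √[(1 + pq·dS²)(1 + pq·dA²)]

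For dS = 3 and dA = 0.6: r = -0.40 / √(3 × 1.08) = -0.40 / 1.80 = -0.22. The simulated mean with nine participants and a fixed 6:3 split is slightly larger in size, at -0.235.

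**Simulation.** There were 200,000 trials per cell, normal data, and SCQ and anxiety independent within each arm. The pooled Pearson test has 7 df. Each cell gives mean r and rejection rate.

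| dA | dS = 2 | dS = 3 | dS = 4 |
|---|---|---|---|
| 0.4 | -0.14, 6.2% | -0.16, 6.9% | -0.17, 7.1% |
| 0.6 | -0.20, 7.9% | -0.24, 9.0% | -0.25, 10.0% |
| 0.7 | -0.23, 8.8% | -0.27, 10.7% | -0.29, 12.0% |
| 1.0 (outside the protocol's range) | -0.31, 12.4% | -0.37, 16.4% | -0.40, 18.6% |
| 1.5 (outside the protocol's range) | -0.43, 20.3% | -0.50, 28.9% | -0.54, 34.2% |

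If dose moves only one of the two variables (dS = 0 or dA = 0), the rate stays at 5%. The excess falls almost entirely on one side: at dA of 0.6 to 0.7, rejections in the direction of more mystical experience with less anxiety occur in about 7% to 11.5% of trials, against a nominal 2.5%.

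**With arm handled.** The partial correlation given arm (6 df) and the correlation in the 25 mg arm alone (4 df) both reject in about 5% of trials in every cell.

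**Price of handling arm.** Critical |r| = t / √(t² + df):
- Pooled: 2.365 / √(5.59 + 7) = 0.67.
- Arm-adjusted: 2.447 / √(5.99 + 6) = 0.71.
- 25 mg arm alone: 2.776 / √(7.71 + 4) = 0.81.

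If the whole dose effect runs through SCQ, power is about 14% pooled against 7% adjusted at dS = 3, dA = 0.6, and about 16% against 7% at dS = 4, dA = 0.7.

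**The averaging test.** For a matched t test with n = 9 and an assumed session difference of 0.6 SD, the noncentrality is 0.6 × √9 = 1.8 on 8 df and power is 0.35. A non-significant result therefore says little about whether the sessions are alike.

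**The case against.** Four points on the other side have weight.

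First, pooling is inferred. The protocol never says that the correlation runs across both arms, and a statistical analysis plan could add arm. That stands as a limit. But the protocol does fix variables and significance level, and it places the correlation directly after a between-arm comparison of the same scores, so pooling is the natural reading.

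Second, a reader might infer that the pooled correlation merely restates the dose effect, or that a third of such trials would give a false finding. The documents do not support that. A rate near 34% needs a 1.5 SD effect on anxiety, more than twice the top of the protocol's range, together with a 4 SD gap on SCQ. At the protocol's values the mean r is well short of the 0.67 needed for significance.

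Third, the protocol speaks of examining an association and does not claim mediation. If dose moves both variables, the pooled association is real in the mixed population and is spurious only as a statement about people given the same dose. That mystical experience drives benefit is a conclusion a reader might draw, not one the protocol states. This narrows the point without removing it, because the pooled result invites that conclusion and cannot bear it.

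Fourth, adjusting for arm discards the between-dose spread in SCQ that the design creates, roughly halving an already small power if SCQ is the true pathway. This stands and belongs with the fix.

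On the averaging test, little harm is shown: with equal session variances and no true association, the size after passing it was 4.97%. The pilot status and very low power are already declared.

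**Conclusion.** The point holds in moderate form. For SCQ, the correlation as worded is confounded by arm if read as pooled. At the protocol's effect of 0.4 to 0.7 SD and an assumed SCQ gap of 2 to 4 SD, with no within-dose link, the 5% test rejects in about 6% to 12% of trials, mostly in the direction that looks like benefit. The bias grows with the dose effect, but larger figures lie outside the protocol's range. The result rests on pooling, two-sided testing, normal data and the assumed SCQ gap.

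The same should not be inferred for SELF: the protocol states no expected dose difference on it and does not say that 4 mg leaves it unchanged. Nor does the protocol say that 4 mg leaves SCQ at zero; it allows slight changes in mood, cognition and perception, which is one reason for showing a range of gaps. The averaging test is a side issue.

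**What to change.** - Correlate change in HADS anxiety from baseline (V3) to V10 with SCQ, adjusted for arm (partial correlation, 6 df). This matches the objective of reduction in anxiety and the baseline-to-two-week contrast of the primary analysis.
- Show the 25 mg participants' data separately.
- Report any pooled correlation as descriptive only, with a statement that it is not evidence that mystical experience drives benefit.
- Label the result exploratory.
- Optionally, always use the two-session mean SCQ and drop the matched t test as a gate.

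This needs no new data, visits or participants. It costs one degree of freedom and, if SCQ truly carries the dose effect, a fall in power from about 14% to 7% at gaps of 3 SD on SCQ and 0.6 SD on anxiety. Neither version can settle the mechanism with nine participants; the adjusted one at least answers the question about experience and not the one about dose.

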Monitoring for Risks

According to the most recent and comprehensive review, serotonergic hallucinogens "are generally considered to be physiologically safe molecules" that chiefly alter consciousness (Nichols 2004). Recent reviews and searches of the literature indicate that psilocybin is not associated with harm or damage to any organ or system in the body

(Nichols 2004; Passie et al. 2002), for more details see “Chemistry and Pharmacology” section in this protocol and sections of the Investigator’s Brochure. Psilocybin can produce changes in blood pressure and heart rate, but these changes are not as strong or as consistent as those seen after psychostimulants or entactogens (MDMA-like drugs), and sometimes these changes only occur at one time point (Griffiths et al. 2006; Hasler et al. 2004). More consistently, psilocybin can produce rapid and intense changes in mood, including periods of anxiety or panic. Both these physiological and psychological effects are transient and do not last beyond the duration of drug effects. Psilocybin is not expected to interact with opiate pain management medication, except to blunt some subjective effects (Grob 2007).

Researchers studying the effects of 30 mg psilocybin took precautions similar to the ones we will use in this study (Griffiths et al. 2006), and no reactions requiring pharmacological intervention occurred.

The investigators will perform a liver panel prior to each psilocybin session to ensure that any recent cancer medications or disease processes have not significantly impaired liver function to the point wherein a participant might have higher than expected psilocybin or psilocin levels. The investigators may reschedule the psilocybin session or withdraw the participant from the study in response to liver panel results.

Acute Psychological Distress

The investigators will discuss possible effects of the study drug with participants during introductory psychotherapy sessions and immediately before each experimental session to reduce the likelihood of a panic response. The intent of psilocybin-assisted psychotherapy sessions is to allow the participant whenever possible to confront and move through intense emotional changes or experiences evinced by psilocybin. Participants will be prepared for confronting emotionally intense thoughts, memories or experiences during the introductory psychotherapy sessions. Preparation includes learning hypnotic induction and diaphragmatic breathing. Both investigator-therapists will remain with the participant for up to six hours after drug administration, or until the participant is mentally stable or has returned nearly or wholly to baseline.

If after eight hours the participant continues to exhibit extreme psychological distress, paranoia or lack of insight into his or her condition, at least one and possibly both therapist-investigators will remain with the participant until his or her anxiety and mental status has returned to baseline. If appropriate, the participant will receive a rescue medication, but with a preference for supportive care first, as described below.

If a participant exhibits signs of psychological distress, panic or psychotic response as described above, the investigators will first remind the participant that he or she has taken a psychoactive drug and that he or she can first stay with and work through the anxiety. The investigators can offer support and reassurance, and they may help reduce anxiety through reminding the participant of the techniques learned prior to the experimental session. Intravenous lorazepam (1 - 3 mg) will also be available for on-site treatment of extreme acute anxiety if needed. Benzodiazepines may be prescribed in the days

following the experimental session, as a supplement to other non-drug methods of reducing anxiety. Sublingual olanzapine (Zyprexa[®], 10 mg) will be available for treatment of psychosis or extreme distress that does not resolve with supportive care. At least one of the investigators will be available by telephone throughout the night after each drug administration.

Rescue medication will only be used if an individual is endangering him or herself or others, or at the discretion of the investigator. The use of prescribed rescue medicines during an experimental session is contraindicated because it can interrupt the therapeutic process, although it would not be expected to cause any physical harm to the subject. The goal of the process is to confront fears and to experience them fully as a means of coping with them, and participants are likely to feel anxious during the course of the experimental session.

The investigators will query subjects about suicidal ideation or intent during screening, and prior to each psilocybin session. Participants who evidence suicidal ideation or intent will be withdrawn from the study and referred to appropriate psychiatric care.

If a psychiatric hospitalization is necessary, participants will be admitted to the study site, which is on the same campus as the clinic. The hospital will be informed in advance about the study.

Medical Emergencies

Basic emergency equipment is available in the cancer center. The principal investigator's office is located in the study site, on the same grounds as the clinic. The hospital will be informed in advance about the nature of this study.

The investigators will assess blood pressure at least five times during the experimental session; immediately prior to drug administration, and hourly for the next three hours. The investigators will make more frequent measures if in their judgment these are warranted. The clinic will have the appropriate medications and equipment to treat hypertension or cardiac problems if they should arise. The slight elevations in blood pressure or heart rate after psilocybin are not expected to cause any problems or cause any adverse events requiring medical intervention.

An adverse event (AE) is defined as any untoward medical occurrence in a patient or clinical investigation subject administered a pharmaceutical product at any dose that does not necessarily have to have a causal relationship with this treatment. An AE can, therefore, be any unfavorable and unintended sign (including an abnormal laboratory finding, for example), symptom, or disease temporally associated with the use of an investigational product, whether or not considered related to the investigational product. This definition includes concurrent illnesses or injuries and exacerbation of pre-existing conditions.

An *unexpected adverse event* is one that is not listed in the current Investigator's Brochure or an event that is by nature more specific or more severe than a listed event.

All AEs will be monitored until resolution or, if the AE becomes chronic, a cause identified. If an AE is unresolved at the conclusion of the study, a clinical assessment will be made by the investigator and Medical Monitor as to whether continued follow-up of the AE is warranted.

The severity of events reported on the “Adverse Events” CRF will be determined by the investigator as:

Mild: no limitation in normal daily activity.

Moderate: some limitation in normal daily activity.

Severe: unable to perform normal daily activity.

The relationship of the study treatment to an AE will be determined by the investigator based on the following definitions:

1. Not Related

The AE is not related if exposure to the investigational product has not occurred, **or** the occurrence of the AE is not reasonably related in time, **or** the AE is considered unlikely to be related to use of the investigational product, i.e. there are no facts (evidence) or arguments to suggest a causal relationship, or the AE is more likely related to the subject's pre-existing condition.

2. Possibly Related

The administration of the investigational product and AE are considered reasonably related in time **and** the AE could be explained by causes other than exposure to the investigational product.

3. Probably Related

Exposure to the investigational product and AE are reasonably related in time **and** the investigational product is more likely than other causes to be responsible for the AE, **or** is the most likely cause of the AE.

The relationship of the study treatment to an AE will be determined by the investigator.

Serious Adverse Events

A serious adverse event (SAE) is defined as any untoward medical occurrence that at any dose:

Results in death

Is life-threatening (i.e., the subject was, in the opinion of the investigator, at immediate risk of death from the event as it occurred); it does not refer to an event which hypothetically might have caused death if it were more severe.

Requires or prolongs inpatient hospitalization

Results in persistent or significant disability/incapacity (i.e., the event causes a substantial disruption of a person's ability to conduct normal life functions)

Results in a congenital anomaly/birth defect

Requires intervention to prevent permanent impairment or damage

Is an important and significant medical event that may not be immediately life threatening or resulting in death or hospitalization but, based upon appropriate medical judgment, may jeopardize the patient/subject or may require intervention to prevent one of the other outcomes listed above.

Adverse events which do not fall into these categories are defined as **non-serious**. It should be noted that a severe adverse event need not be serious in nature and that a serious adverse event need not, by definition, be severe.

In addition, a pre-existing event or condition that results in hospitalization should be recorded on the medical history. The hospitalization would not result in the event or condition being reported as an on study SAE unless, in the view of the investigator, hospitalization was prolonged as a result of participation in the clinical trial or was necessary due to a worsening of the pre-existing condition. This is because the onset of the event (the reason for the procedure) occurred before the subject was entered in the trial. Hospitalization for cosmetics, non-emergency prophylaxis or abortion does not result in an SAE report unless, in the view of the investigator, hospitalization for these procedures was prolonged as a result of participation in the clinical trial.

Adverse Event Collection

All serious adverse events will be collected for the duration of the study. All SAEs which occur during the course of the trial, whether considered to be associated with the study IP or not, have to be reported **within 24 hours** or at the latest on the following working day by telephone or fax to either of the following:

Medical Monitor: [name] [contact] [contact]

Study Monitor: [name] [contact]; [name]

Adverse events that will be collected for the duration of the study are:

Pain using the VAPS.

Events requiring a physician visit or an intervention, not related to planned treatments for baseline conditions.

Any adverse event leading to withdrawal from the study.

Additional adverse events collected for seven days after each experimental session are:

Common side effects.

Exacerbation of anxiety.

Collection of Concomitant Medications

All prescription concomitant medications will be recorded at baseline. During the study participants will keep a daily log of medications taken while actively enrolled in the study protocol. Only changes to anxiolytic and pain management baseline medications will be recorded on the CRF.

Laboratory Assessments

Before the study, the investigator will supply the sponsor with a list of the normal ranges for clinical laboratory assessments. All abnormal laboratory values require a comment from the investigator on the laboratory report, regardless of the clinical significance.

After reviewing the laboratory report and evaluating any results that are outside the normal range, the investigator must sign and date the laboratory report. Any abnormal laboratory test result that warrants further investigation to guard the subject's safety will be repeated as appropriate and reviewed by the investigator.

Study Monitoring, Auditing and Documentation

Investigators and/or their study staff will be trained during the initiation visit. During each monitoring visit, source data verification will be performed by qualified staff representing the sponsor. A CRF collation supplied by the sponsor will be completed for each subject. The entries will be checked by trained delegates of the sponsor.

Monitoring and auditing procedures of the sponsor will be followed, in order to comply with GCP guidelines and to ensure validity of the study data.

The sponsor will review the study documentation used for planning, conduct and monitoring of the study in order to ensure compliance with GCP and local regulations. This documentation includes as a minimum: the Investigator's Brochure, the Study Protocol, the Case Report Forms and the Subject Information and Consent Form.

Risks to Participants

Risks and Discomforts Related to Screening and Baseline Examination

All participants must first give permission for the investigators to review medical records and later undergo a psychiatric evaluation and a urinary drug screen to ensure that participants are eligible to be in the study. Permitting the investigators to view their medical test results slightly increases the likelihood of a potential breach of confidentiality, but doing so is necessary for screening appropriate candidates for the study. The investigators will store any information in locked file cabinets within a locked office, as described in "Confidentiality." Participants may find discussing their anxiety and their illness during the psychiatric evaluation upsetting, or they may find screening boring or tiring. Screening is necessary to assess participant eligibility. Participants will have to provide urine for a drug screen, and they may be embarrassed or uncomfortable about the procedure. The urinary drug screen is necessary for verifying the participant's report of current substance use.

Participants will complete self-report and clinician-administered measures of anxiety, depression, quality of life, and spirituality at baseline and during nearly every visit throughout the course of the study, including prior to each psilocybin session and the follow-up two weeks after the second experimental session. Participants may find completing these measures upsetting, or they may find them boring or tiring. The measures are necessary to assess anxiety and depression, quality of life and changes in world view, self-concept and presence of mystical experiences.

Risks and Discomforts of Psychotherapy

During non-drug and experimental sessions, participants will be asked to think about and discuss their thoughts and emotions about their illness, including anxiety and the impact the illness has had on their lives. They may experience intense emotional responses to speaking about these thoughts, feelings and concerns. Even in a therapeutic context, thinking about and discussing serious illness and impending death or the effects of disease progression on life function can produce distress during and immediately after psychotherapy. Psychotherapy is conducted as part of the research study, including the experimental intervention (psilocybin-assisted psychotherapy), and people undergoing psychotherapy are expected to confront unpleasant thoughts, feelings and memories in the process of therapy. They will also learn to use several procedures in coping with anxiety and distress as part of psychotherapy. Because psychotherapy is an integral part of the research study design, the potential distress arising from psychotherapy is unavoidable.

Risks and Discomforts of Procedures Prior to Psilocybin Session

Participants will undergo a blood draw for a standard liver panel prior to each psilocybin session to ensure that they possess sufficient liver function to metabolize psilocybin. The blood draw may produce temporary discomfort as a result of sampling blood. Participants may also experience temporary discomfort at the blood drawing site. There is also a remote possibility of inflammation or infection at the blood drawing site. Liver panel results will allow the investigators to detect poor metabolism, which could produce higher than expected levels of psilocybin. Higher levels of psilocybin may produce prolonged duration or greater intensity of subjective effects. Weighing the risks and benefits of a blood draw versus potentially unpredictable levels of psilocybin, the liver panel conveys more benefits than risks.

Participants will also undergo urinary pregnancy and drug screens. Some participants may be uncomfortable with this procedure or discussing the test results. However, it is necessary to assess pregnancy to avoid the risk of unintended psilocybin exposure in utero. The urinary drug screen is necessary to verify that people have abstained from cocaine or nonprescription stimulants upon study enrollment or prior to each psilocybin session.

Risk of the Experimental Drug (psilocybin)

Psilocybin given at the full dose can be expected to alter affect (mood), cognition (thought) and perception. Common side and adverse effects of psilocybin are listed in “Safety Pharmacology” in the Pharmacology section, and include anxiety, changes in

thought speed or content, depersonalization, derealization, dizziness, fatigue, inattention, impaired concentration, labile mood, nausea, paresthesias, altered time perception, altered visual perception, and unusual thoughts. Psilocybin also produces pupillary dilation and can produce changes in blood pressure and heart rate. These effects are transient and are generally gone approximately six hours after drug administration. People in previous human studies have tolerated doses of psilocybin equal to or greater than the doses employed in this study.

Like other serotonergic psychedelics, psilocybin can produce a number of psychological adverse events, most of them related to increased anxiety or psychological distress. The likelihood of these effects occurring during a controlled study is far lower than during nonmedical use (Halpern and Pope 1999; Hasler et al. 2004). However, the investigators will whenever possible take the steps below to further reduce or prevent their occurrence.

Panic attacks, severe generalized anxiety, or persisting insomnia

Psilocybin can produce anxiety and/or panic response, and less commonly, a prolonged unpleasant experience (or “bad trip”), as can other serotonergic psychedelics, such as LSD. Medical case reports and case series specific to consumption of psychedelic mushrooms (Hyde et al. 1978; Musha et al. 1986; Peden and Pringle 1982) report that emergency department admissions after use of psilocybin-containing mushrooms report transient anxiety or panic. The most commonly reported adverse events described in a survey of 44 individuals admitted to hospital after psilocybin use were dysphoria that lasted for an average of 3.8 hours, followed by nausea or vomiting, occurring in almost half the admissions (Peden and Pringle 1982).

